5.3. Lifestyle Considerations

5.3.1. Contraception

Women of childbearing potential must agree to take appropriate precautions to avoid pregnancy from screening through 30 days after the last dose of encorafenib.

Male participants must agree to take appropriate precautions to avoid fathering a child and prevent exposure of seminal fluid to the partner from screening through 90 days after the last dose of encorafenib.

The methods of contraception outlined in Appendix 10.2.2 are permitted under this protocol for use by the participant and his/her partner. These methods should be communicated to the participants and their understanding confirmed.

Note: Due to the potential of encorafenib to induce CYP3A4, hormonal agents (including but not limited to birth control patch, vaginal ring, oral, injectable or implanted contraceptives) are permissible only when combined with other highly effective methods of contraception.

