6.5.1.1. Authorized Therapies requiring Caution and/or Action

Participants should be closely monitored for the occurrence of adverse events whilst taking these therapies.

6.5.1.1.1. *Cytochrome P450 and Uridine 5'-diphospho-glucuronosyltransferase Substrates and Inhibitors*

Encorafenib is a reversible inhibitor of CYP2B6, CYP2C9, CYP3A4 and uridine 5'-diphospho-glucuronosyltransferase (UGT)1A1. It is also a time-dependent inhibitor of CYP3A4. Permitted medications to be used with caution in this study include those that are sensitive substrates of CYP2B6, CYP2C8, CYP2C9, CYP2C19, CYP3A4 (see Table 11 and Table 12) and UGT1A1 (see Table 13) or those substrates that have a narrow therapeutic index.

There is a potential for encorafenib to induce CYP3A4, which may reduce the effectiveness of hormonal contraception methods. At least one form of non-hormonal contraception is therefore required during participation in this study (see Section 5.3.1). Caution should also be exercised in participants receiving concomitant treatment with other drugs that are substrates of CYP3A4 as the efficacy of these drugs could be reduced when administered with encorafenib.

Encorafenib has been identified in vitro to be metabolized by CYP3A4 and to a lesser extent by CYP2C19. The use of strong inhibitors of CYP3A4 is prohibited (see Section 6.5.2). Concomitant use of moderate CYP3A4 inhibitors (see Table 14) while on study should be avoided. If use of moderate CYP3A4 inhibitors is unavoidable and no alternatives are available, short-term use (≤ 30 days) following discussion with the sponsor may be permitted with accompanying dose reduction to one-half of the encorafenib dose before use of moderate CYP3A4 inhibitors (or as close as can be achieved without exceeding the target dose). The encorafenib dose that was taken before initiating the CYP3A4 inhibitor may be resumed after the inhibitor has been discontinued for three to five elimination half-lives. Strong inhibitors of CYP2C19 should be used with caution when coadministered with encorafenib.

6.5.1.1.2. *Transporter Substrate and Inhibitors*

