10.2.2. Contraceptive Guidance

For the purpose of this guidance, methods that can achieve a failure rate of less than 1% per year when used consistently and correctly are considered as highly effective birth control methods. Such methods include:

- Combined (estrogen and progestogen containing) hormonal contraception associated with inhibition of ovulation:
 - Oral.
 - Intravaginal.
 - Transdermal.
- Progestogen-only hormonal contraception associated with inhibition of ovulation:
 - Oral.
 - Injectable.
 - Implantable.
- Intrauterine device.
- Intrauterine hormone-releasing system.
- Bilateral tubal occlusion.
- Vasectomized partner.
- Sexual abstinence.

Acceptable birth control methods that result in a failure rate of more than 1% per year include:

- Progestogen-only oral hormonal contraception, where inhibition of ovulation is not the primary mode of action.
- Male or female condom with or without spermicide.
- Cap, diaphragm or sponge with spermicide.

NOTE: Due to the potential of encorafenib to induce CYP3A4, hormonal agents (including but not limited to birth control patch, vaginal ring, oral, injectable or implanted contraceptives) are permissible only when combined with other highly effective or acceptable methods of contraception.

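### Section 5.3.1 and Appendix 10.2.2 disagree on whether a barrier method may accompany hormonal contraception

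*Protocol*

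**What the plan says.** Three places in the protocol deal with hormonal contraception during encorafenib treatment.

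- **Section 5.3.1** says that hormonal agents are "permissible only when combined with other highly effective methods of contraception". It also says: "The methods of contraception outlined in Appendix 10.2.2 are permitted under this protocol for use by the participant and his/her partner". Sites are then told: "These methods should be communicated to the participants and their understanding confirmed".
- **Appendix 10.2.2** ends with a note that is nearly the same as the one in Section 5.3.1, except that hormonal agents are "permissible only when combined with other highly effective or acceptable methods of contraception". The appendix sets the upper class by this definition: "methods that can achieve a failure rate of less than 1% per year when used consistently and correctly are considered as highly effective". The lower class is introduced with the words "Acceptable birth control methods that result in a failure rate of more than 1% per year include".
- **Section 6.5.1.1.1** gives the pharmacological reason: "There is a potential for encorafenib to induce CYP3A4, which may reduce the effectiveness of hormonal contraception methods". It concludes that one or more non-hormonal methods are needed during the study and refers to Section 5.3.1.

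Inclusion criterion 13 (Section 5.1) asks women of childbearing potential to agree to highly effective contraception from screening to 30 days after the last dose.

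**The concern.** The two notes serve the same purpose and differ in substance only by the words *or acceptable*. Those words change the answer for a realistic case: a woman on a hormonal method whose second method is a barrier. Section 5.3.1 refuses the combination and Appendix 10.2.2 permits it.

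What is at stake is consistent counselling on a safety precaution. The study runs at two or three sites, and staff who rely on different passages would advise differently. A woman advised from the appendix could depend on a hormonal method that the drug may weaken, plus a second method that does not itself meet the below-1% definition. The documents give no failure rate for such a combination, so the size of any added risk is unknown.

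**Working it through.** The plan gives no figure to reproduce. The check sets the passages side by side and then applies them to the methods listed in Appendix 10.2.2.

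**Step 1: the rules.**

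| Passage | Companion required | Effectiveness level | Expressly non-hormonal? |
|---|---|---|---|
| Section 5.3.1 | another highly effective method | below 1% per year | no |
| Appendix 10.2.2 note | another highly effective or acceptable method | below or above 1% per year | no |
| Section 6.5.1.1.1 | at least one non-hormonal method | not stated | yes |

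**Step 2: the listed methods.** Appendix 10.2.2 has 7 highly effective lines and 3 acceptable lines.

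- Highly effective and hormonal, 3 lines: combined hormonal; progestogen-only that inhibits ovulation; "Intrauterine hormone-releasing system".
- Highly effective and non-hormonal, 7 − 3 = 4 lines: intrauterine device, bilateral tubal occlusion, vasectomized partner, sexual abstinence.
- Acceptable and hormonal, 1 line: the progestogen-only pill that does not act mainly by inhibiting ovulation.
- Acceptable and non-hormonal, 3 − 1 = 2 lines: condom; cap, diaphragm or sponge with spermicide.

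This treats the intrauterine device line as non-hormonal, because the hormone-releasing system has a line of its own.

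**Step 3: apply the rules to non-hormonal companions.** There are 4 + 2 = 6 such lines.

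- Section 5.3.1 accepts the 4 highly effective lines.
- Appendix 10.2.2 accepts 4 + 2 = 6.
- In dispute: 6 − 4 = 2, the two barrier lines.

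**Step 4: does the result depend on how Section 5.3.1 is read?** The word *other* in that note most naturally means other than hormonal agents. If it is read only as *another*, Section 5.3.1 would also accept a second hormonal method from the upper class. It would still refuse both barrier lines, because neither is in that class. The disagreement over barrier methods holds on either reading.

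**Step 5: is there a rule that fits all three passages?** Yes. The 4 lines that are both highly effective and non-hormonal satisfy Sections 5.3.1 and 6.5.1.1.1 and Appendix 10.2.2 together.

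**The case against.** The best reply is that Section 5.3.1 governs. Sections 6.5.1.1.1 and 8.4.5 both point to it for the contraceptive requirements, its standard matches inclusion criterion 13, and the clinical research associate trains sites on protocol requirements at initiation. This carries some weight, but it does not settle the matter. Section 5.3.1 itself passes the reader on to Appendix 10.2.2 for the permitted methods, and the appendix carries the looser note. The sponsor may even have intended hormonal plus barrier, which would also meet the non-hormonal requirement in Section 6.5.1.1.1.

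A reader might go further and infer three mutually incompatible rules, with a pill plus a hormone-releasing intrauterine system as a second contradictory case. The documents do not support that. Section 6.5.1.1.1 sets a non-hormonal floor, says nothing about effectiveness, and can be read together with Section 5.3.1. A hormone-releasing system is itself a hormonal agent, so on the natural reading of *other* it is not a companion method at all. For the same reason, a headline such as four of nine companions accepted by every passage should not be used: the denominator is a choice of grouping and could as well be eight or six.

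A reader might also infer an eligibility failure. Criterion 13 asks for agreement to use contraception, and the advice can be corrected during screening or treatment.

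The exposure is also limited. Section 8.3.5 requires negative pregnancy tests at screening and before dosing on Cycle 1 Day 1, with urine tests on Day 1 of each cycle from Cycle 2. Testing detects pregnancy but does not prevent it.

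**Conclusion.** The protocol contradicts itself on one practical question: whether a condom, or a cap, diaphragm or sponge, suffices alongside a hormonal method. Section 5.3.1 says no, Appendix 10.2.2 says yes, and nothing says which prevails. In addition, the non-hormonal requirement in Section 6.5.1.1.1 is attributed to Section 5.3.1, where it is at most implied.

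The severity is minor. The conflict covers two method lines. It does not affect the DLT analysis or any other statistical quantity. The number of women concerned is not stated and may be zero among up to six evaluable participants. The rules can all be met at once, so this is an inconsistency and not an impossible requirement. The conclusion rests on the wording of the two notes; the count also assumes that the intrauterine device line is non-hormonal.

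**What to change.** For participants taking encorafenib, delete *or acceptable* from the Appendix 10.2.2 note and use one sentence in Sections 5.3.1 and 6.5.1.1.1 and Appendix 10.2.2: *Hormonal agents are permissible only when combined with a non-hormonal highly effective method of contraception.* Inclusion criterion 13 may refer to it.

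Do not extend the sentence to inclusion criterion 14. The CYP3A4 reason applies to the person who takes the drug, and a male participant's partner is not dosed.

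The cost is a wording change at three places, plus an optional cross-reference, at the next amendment with IRB/IEC approval (Section 10.1.1). There are two downsides. Women using hormonal plus barrier contraception must change their second method. Hormonal methods would no longer count on their own towards the requirement, since each permitted companion already qualifies alone.

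If the sponsor intends to allow barrier companions, the alternative is to amend Section 5.3.1 so that the passages agree. That means accepting a second method above the 1% line.

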5.3.2. Meals and Dietary Restrictions

Participants must refrain from the consumption of grapefruit, pomegranates, star fruits, Seville oranges, lime, sour orange, citrus depressa, other local fruits or products containing the juice of any of these items from 7 days before the start of study treatment until after the final dose due to potential CYP3A4 interaction with encorafenib (see **Section 6.5.1**). Orange juice is allowed.

There are no restrictions on dosing or PK sampling in relation to the timing of meals.

5.4. Screen Failures

Screen failures are defined as participants who sign the ICF but fail to meet one or more criteria required for participation in the study or do not complete the screening process. A minimal set of screen failure information is required to ensure transparent reporting of screen failure participants to competent authorities.

The following will be recorded in the electronic case report form (eCRF) for screen failures:

- Date of informed consent.
- Review of inclusion/exclusion criteria.
- Adverse events related to a study procedure during the screening period and any medications used to treat those adverse events.

Participants who do not meet the criteria for participation in this study (screen failure) cannot be rescreened. However, if vital signs measured as per protocol do not initially fulfil inclusion criterion, an unscheduled assessment is authorized after 10 minutes of rest without considering this as rescreening.

6. Study Treatment

6.1. Study Treatment(s) Administered

The study treatment is encorafenib, a novel, oral, highly selective ATP-competitive small molecule kinase inhibitor with potent and selective inhibitory activity against mutant BRAF kinase, a member of the RAS/RAF/MEK/ERK pathway, which plays a prominent role in controlling several key cellular functions including growth, proliferation and survival in tumor cells expressing metastatic *BRAF* V600E mutations, including melanoma and lung cell lines.

Encorafenib treatment details are provided in Table 5. Full information is provided in the Pharmacy Manual and the Investigator's Brochure for encorafenib.

Table 5: Detail of Study Treatment

Study treatment	Encorafenib
Code	PF-07263896 or W0090 (in Europe), LGX818 (in US), ONO-7702 (in Japan).
Pharmaceutical form	Hard capsule
Dosing regimen	Flat-fixed dose
Route of administration	Oral
Unit dose Components	Active ingredient: encorafenib. Inactive excipients: copovidone, poloxamer 188, succinic acid, microcrystalline cellulose, silica colloidal anhydrous, crospovidone, and magnesium stearate. The capsule shell is commercially available and contains: gelatin, titanium dioxide (E171), iron oxide red (E172), iron oxide yellow (E172), iron oxide black (E172), ink capsule shell (pharmaceutical glaze, iron oxide black (E172) propylene glycol).
Strength	75 mg
Dose	300 mg (4 × 75 mg)
Frequency	QD
Abbreviations: QD = once daily; US = United States.	

Encorafenib will be supplied by the sponsor and sent to a local facility (sponsor designee) for storage prior to onward distribution to each study site prior to, and during the study.

The study treatments will be packaged and labelled by the Investigational Medicinal Product Management Service of IRPF according to local requirements and local language(s). Each study treatment box is labelled, at a minimum, with the rules described in **Appendix 6: Study Treatment labelling**.

Encorafenib 75 mg will be packaged into a box of 120 hard capsules. This box will contain 20 blisters of six capsules.

Encorafenib will be orally self-administered. A fixed-flat dose of 300 mg PO encorafenib will be administered QD. Encorafenib should be taken daily in the morning at approximately the same time (\pm 2 hours) every day without regard to food. If a participant vomits at any time after dosing, the dose should not be re-administered. Doses of encorafenib that are omitted for adverse events or any other reason should not be made up during the day, or at the end of the dosing period.

The first dose of encorafenib will be taken on Cycle 1 Day 1 and will then be continuously self-administered in 28-day cycles until death, disease progression, one of the other criteria for study treatment discontinuation is met (see Section 7.1) or the participant is lost to follow-up (see Section 7.3). On Day 1 of each cycle the encorafenib dose will be administered at the study site.

Lifestyle considerations in relation to dosing are detailed in Section 5.3. There are no restrictions on dosing in relation to the timing of meals.

Participants will receive a diary to document self-administration of encorafenib to include the dose, date of dosing (and time if applicable), if the participant vomited after dosing, if any doses were missed and the reason for the missed dose. One diary will be provided per cycle. On the days when encorafenib is administered at the study site, these details will be recorded in the eCRF by the study site personnel.

Management of dose modifications (including dose interruptions and retreatment) are detailed in Section 6.6.

Continuing study treatment beyond disease progression for any participant is only to be considered under special circumstances when it is believed that the participant may clinically benefit from continued treatment beyond progression. If it is judged by the investigator (in consultation with the sponsor) to be in the best interest of the participant, the participant may remain on study treatment as long he/she continues to benefit from the study treatment according to the investigator's assessment. Special circumstances can be defined by e.g. mixed responses and appearance of new brain metastases (only) which is treatable with stereotactic radiotherapy or surgery but does not require whole brain radiotherapy.

Treatment beyond progression is not allowed in the following cases:

- Participants with clear evidence of disease radiographic and clinical progression at multiple sites or clear evidence of new lesions outside the central nervous system.
- Participants with rapid progression of disease at critical anatomical sites (e.g. cord compression) requiring urgent alternative medical treatment cannot be dosed beyond progression.
- Participants who have clinically relevant worsening of laboratory values.
- Participants who have a clinically significant decline in ECOG performance status at time of progression.

6.2. Preparation/Handling/Storage/Accountability/Return/Destruction

6.2.1. Accountability on Site and Return/Destruction

Before the start of the study, the sponsor or designee will supply the study site with the number of study treatments units required for the study using Interactive Response Technology (IRT).

Encorafenib will be supplied by the sponsor and sent to a local facility (sponsor designee) for storage prior to onward distribution to each study site prior to, and during the study. Full shipping, storage and handling details will be provided in the Pharmacy Manual.

- Labelled, packaged encorafenib will be shipped to each study site by the sponsor designee and will contain a temperature monitoring device. The investigator or designee must confirm appropriate temperature conditions have been maintained during transit for all study treatment received and any discrepancies are reported and resolved before use of the study treatment.
- Only participants enrolled in the study may receive study treatment and only authorized study site personnel may supply or administer study treatment. All study treatment must be stored according to Section 6.2.2.
- The investigator, institution or the head of the medical institution (where applicable) is responsible for study treatment accountability, reconciliation and record maintenance (dates and quantities of study treatment received, to whom study treatment is dispensed [participant-by-participant accounting] and accounts of returned and destroyed treatment).

To ensure adequate records, all study treatment will be accounted for on an accountability inventory form as instructed by the sponsor according to Good Clinical Practice (GCP) (International Council on Harmonization [ICH] E6 (R2) [5.14]).

Drug accountability must be performed by the clinical research associate (CRA) on a regular basis during the study according to the Monitoring Plan. The investigator must retain all unused or expired study treatment supplies until the CRA has confirmed the accountability records. If site policy prohibits holding study treatment supplies for CRA review, then a copy of the standard operating procedure for processing returns must be provided to the sponsor.

- At the end of the study, all used and unused study treatment including packaging should be noted and return/destruction is organized by the CRA. Further guidance and information for the final disposition of unused study treatments are provided in the Pharmacy Manual.

6.2.2. Storage

At the time of delivery to the site an accompanying letter will be provided with the details of storage conditions that should be respected.

As soon as the Pharmacist receives the study treatment, he/she will check the contents and immediately follow the instructions described in the Study Pharmacy Manual. Documents included in the parcel will be kept in the Investigator's file. .

At the time of delivery to the site an accompanying letter will be provided with the details of storage conditions that should be respected. The CRA will ensure during the initiation visit that study treatments have been received in good conditions and the acknowledgment of receipt has been returned adequately.

All study treatment must be stored in a secure, environmentally controlled and monitored (manual or automated) area in accordance with the labelled storage conditions and applicable regulatory requirements with access limited to the investigator and authorized study site personnel.

Storage conditions will be described on the medication label. Detailed instructions for storage and handling of encorafenib will be detailed in the Study Pharmacy Manual.

6.2.3. Expiry Date

The investigator or designee should ensure that the study treatment expiry date has not been exceeded. If the expiry date has been exceeded, then the affected study treatment supplies must be quarantined to prevent them from being used. Accountability and final disposition will follow the process in Section 6.2.1.

6.2.4. Return / destruction

At the end of the study, all used and unused study treatments, including packaging should be tracked, and their return/destruction will be arranged by the CRA.

The study treatment can be destroyed at the sponsor-designated local facilities or at a third party (on site) in accordance with local guidelines, as appropriate.

Further guidance and information for the final disposition of unused study treatments will be provided in the Study Pharmacy Manual.

6.2.5. Recall

In case of recall of study treatment (decided by the competent authorities or the sponsor), the investigator will be immediately informed by the sponsor. The investigator, in collaboration with the sponsor representatives (study manager, CRA) must urgently:

- Put all study treatments concerned by the recall in quarantine.
- Stop the administration of the concerned study treatments to the participants.

- Inform the concerned participants that they must immediately stop taking these study treatments and bring them back.

The study manager/CRA will organize the return of the recalled products to Pierre Fabre Médicament, according to the sponsor procedures.

